5.5.6. Analysis Related to HS-IGA

- The proportion of participants with HS-IGA score of inactive (0), HS-IGA score of inactive (0) or almost inactive (1), and the proportion of participants achieving HS-IGA score of mild activity or better (≤ 2) and with at least 2-grade improvement relative to baseline at Week 16 will be compared between each of the guselkumab groups and the placebo group.
- The proportion of participants with HS-IGA score of inactive (0), HS-IGA score of inactive (0) or almost inactive (1), and the proportion of participants achieving HS-IGA score of mild activity or better (≤ 2) will be summarized by treatment groups over time. In addition, the proportion of participants with 1 -grade and 2-grade improvement in HS-IGA scores from baseline will be summarized over time respectively.
- The proportion of participants with HS-IGA score of inactive (0), almost inactive (1) at Week 16 among participants with HS-IGA score of moderate activity (3) or severe activity (4) at baseline will be compared between each of the guselkumab groups and the placebo group and will also be summarized by treatment groups over time.

- The proportion of participants with HS-IGA erythema score of (0), erythema score of (0) or (1), and the proportion of participants with HS-IGA erythema score of light red color or better (≤ 2) at Week 16 will be compared between each of the guselkumab groups and the placebo group and will also be summarized by treatment groups over time.
- The proportion of participants with HS-IGA erythema score of 0, erythema score of 0 or 1, and the proportion of participants with HS-IGA erythema score of light red color or better (≤ 2) will be summarized by treatment groups over time.
- The proportion of participants with HS-IGA drainage score of 0, drainage score of 0 or 1, and the proportion of participants with HS-IGA drainage score of mild spontaneous drainage or better (≤ 2) at Week 16 will be compared between each of the guselkumab groups and the placebo group and will also be summarized by treatment groups over time.
- The proportion of participants with HS-IGA drainage score of 0, drainage score of 0 or 1, and the proportion of participants with HS-IGA drainage score of mild spontaneous drainage or better (≤ 2) will be summarized by treatment groups over time.
- The proportion of participants with HS-IGA pain and/or tenderness to gentle palpation (excluding scarring area) score of 0, score of 0 or 1, and the proportion of participants with HS-IGA pain and/or tenderness to gentle palpation (excluding scarring area) score of mild pain and/or tenderness with palpation or better (≤ 2) at Week 16 will be compared between each of the guselkumab groups and the placebo group and will also be summarized by treatment groups over time.
- The proportion of participants with HS-IGA pain and/or tenderness to gentle palpation (excluding scarring area) score of 0, score of 0 or 1, and the proportion of participants with HS-IGA pain and/or tenderness to gentle palpation (excluding scarring area) score of mild pain and/or tenderness with palpation or better (≤ 2) will be summarized by treatment groups over time.

In addition, an IGA score derived from the evaluation for erythema, drainage, and pain and/or tenderness to palpation will be summarized over time.

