2.5. Definition of Subgroups

To evaluate the consistency in the primary efficacy endpoint (proportion of participants who achieve HiSCR at Week 16) over demographics, baseline characteristics, prior and baseline medication use, subgroup analyses will be performed when sample sizes are permitted. The subgroups include, but are not limited to, the following:

Baseline demographics:

- Sex (male, female)
- Race
- Baseline Age (<40 years, 40 to <65 years, ≥65 years)
- Baseline weight (≤95 kg, >95 kg)
- BMI (Normal [<25], Overweight [$25 - <30$], Obese [≥ 30])

Baseline disease characteristics:

- Baseline Hurley stage status (I, II, and III)
- Age at diagnosis (years) (< median, ≥ median)
- HS disease duration (years) (< median, ≥ median)
- Baseline high-sensitivity C-reactive protein (hs-CRP) (< median, ≥ median)
- Baseline AN count category (3 to 5, 6 to 10, ≥11)
- Baseline AN count (< median, ≥ median)
- Baseline HS-IGA (<3, 3, 4)

HS medication and surgery history:

- Systemic immunomodulatory biologics (adalimumab, infliximab, other-anti-TNF inhibitors, ustekinumab)
 - Never used
 - Ever Used

- Hidradenitis Suppurativa related surgery (Deroofing Surgery, Laser Surgery, Excision Surgery)
 - Never had
 - Ever had

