5.5.5. Analysis Related to Lesion Count

AN Count

- The change from baseline in total AN count, the change from baseline in total AN count by weight, and the change from baseline in total AN count by Hurley stage status will be summarized by treatment groups over time.
- The proportion of participants achieving at least 50%, 75%, 90%, and 100% reduction in total AN count at Week 16 will be compared between each of the guselkumab groups and the placebo group.
- The proportion of participants achieving at least 50%, 75%, 90%, and 100% reduction in total AN count will be summarized by treatment group over time.
- The proportion of participants achieving AN count of 0, 0/1, and 0/1/2 respectively at Week 16 will be compared between each of the guselkumab groups and the placebo group.
- The proportion of participants achieving AN count of 0, 0/1, and 0/1/2, respectively will be summarized by treatment group over time.
- The proportion of participants who experience at least one flare (defined as at least a 25% increase in AN count with a minimum increase of 2 AN relative to baseline) over 16 weeks will be compared between each of the guselkumab groups and the placebo group at Week 16. Furthermore, the proportion of participants who experience at least one flare over 48 weeks will be summarized at Week 48 by treatment groups.

In addition, the change from baseline in AN count by prespecified anatomic region and treatment group will be summarized at Week 16 and Week 40.

Abscess

- The proportion of participants who achieved complete elimination of abscesses at Week 16 will be compared between each of the guselkumab groups and the placebo group among participants who had any abscess at baseline.
- The change from baseline in number of abscesses at Week 16 will be compared between each of the guselkumab groups and the placebo group.

- The change from baseline in number of abscesses will be summarized by treatment group over time.

Fistulas

- The proportion of participants who achieved complete elimination of draining fistulas at Week 16 will be compared between each of the guselkumab groups and the placebo group among those with draining fistulas at baseline.
- The change from baseline in number of draining fistulas at Week 16 will be compared between each of the guselkumab groups and the placebo group.
- The change from baseline in number of draining fistulas will be summarized by treatment group over time.

Inflammatory and non-inflammatory Nodules

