- The proportion of participants who achieved complete elimination of inflammatory nodules at Week 16 will be compared between each of the guselkumab groups and the placebo group among those with inflammatory nodules at baseline.
- The change from baseline in number of inflammatory nodules at Week 16 will be compared between each of the guselkumab groups and the placebo group.
- The change from baseline in number of inflammatory nodules will be summarized by treatment group over time.
- The change from baseline in number of non-inflammatory nodules at Week 16 will be compared between each of the guselkumab groups and the placebo group among pts with non-inflammatory nodules at baseline.
- The change from baseline in number of non-inflammatory nodules will be summarized by treatment group over time.

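### HS-IGA threshold comparisons at Week 16 ignore the baseline score, so they mix improvement with maintenance and lose some precision

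*SAP*

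**What the plan says.** SAP 5.5.6 plans Week 16 comparisons of each guselkumab group with placebo at scores 0, 0/1 and ≤2 for three components:

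- erythema, up to "the proportion of participants with HS-IGA erythema score of light red color or better";
- drainage, up to "the proportion of participants with HS-IGA drainage score of mild spontaneous drainage or better";
- pain/tenderness, up to a "score of mild pain and/or tenderness with palpation or better".

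None of these carries a baseline condition or a minimum improvement. The first bullet of the section also compares overall HS-IGA 0 and 0/1 without a baseline condition; the two-grade improvement there is attached to the ≤2 category.

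SAP 5.5.2.1 specifies a CMH test stratified by baseline weight and Hurley stage, with missing responses counted as non-response. SAP 5.2.3.2 makes treatment failures non-responders. Protocol 5.1 requires an AN count of at least 3 and sets no minimum for HS-IGA or its components. SAP 2.5 lists the subgroup "Baseline HS-IGA (<3, 3, 4", so overall scores below 3 at baseline are foreseen.

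Other threshold endpoints do use baseline. Abscess elimination is assessed "among participants who had any abscess at baseline", fistula elimination "among those with draining fistulas at baseline", and nodule elimination "among those with inflammatory nodules at baseline". A further HS-IGA 0/1 comparison is limited to baseline 3 or 4, and the DLQI and HADS thresholds (SAP 5.5.7) also have baseline conditions.

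**The concern.** A participant with no drainage at Week 0 and none at Week 16 is a responder for drainage 0 in either arm. A participant who goes from severe drainage to none is counted the same way. The reported proportion therefore cannot be read as a response rate, and it is not comparable with the fistula result a page earlier, which is limited to people who had fistulas.

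The second consequence is statistical. Baseline status is likely to predict Week 16 status strongly, and it is already collected. A test that ignores it leaves avoidable variance in the comparison. The count is 3 components × 3 cut-offs × 2 doses = 18 comparisons, plus 2 overall scores × 2 doses = 4, so 22 in all.

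**Working it through.** **Inputs from the documents.** 60 per arm and two-sided 0.05 (Protocol 9.2, SAP 1.4, SAP 5.5.2). No power, effect size or baseline distribution is given for any HS-IGA component.

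**Reproducing the plan's own power figure.** For HiSCR 25% versus 55%, power = Φ[(Δ − 1.96·SE₀)/SE₁].

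- SE₀ = √(2 × 0.40 × 0.60/60) = 0.0894
- SE₁ = √((0.1875 + 0.2475)/60) = 0.0851
- (0.30 − 0.1753)/0.0851 = 1.46, so power is 92.9%. Table 1 states 93%.

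**Assumptions for the illustration.** A share q is at target at baseline. Of these, 90% are at target at Week 16 in both arms. Among the rest the rates are 30% on placebo and 55% on guselkumab.

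**Expected rates as planned.** Rate = 0.9q + (1 − q)p, so the difference is (1 − q) × 25 points.

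- q = 10%: 36.0% versus 58.5%, 22.5 points
- q = 20%: 42.0% versus 62.0%, 20.0 points
- q = 40%: 54.0% versus 69.0%, 15.0 points

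**What stratification changes.** With q balanced by randomization, the stratified difference has the same expectation. The gain comes from removing between-stratum variance. At q = 40%:

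- Unstratified: √((0.54 × 0.46 + 0.69 × 0.31)/60) = √(0.4623/60) = 0.0878
- Stratified, placebo variance: 0.4 × 0.09 + 0.6 × 0.21 = 0.1620
- Stratified, guselkumab variance: 0.4 × 0.09 + 0.6 × 0.2475 = 0.1845
- Stratified SE: √(0.3465/60) = 0.0760
- 0.15/0.0878 = 1.71 and 0.15/0.0760 = 1.97, giving power of about 40% and 50%

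**Simulated power (CMH tests).** The ranges cover separate simulation runs; the lower ends include weight and Hurley stage in the strata. The last column uses the normal approximation with 60(1 − q) per arm.

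| At target at baseline | As planned | Baseline status added as stratum | Restricted to above target |
|---|---|---|---|
| 10% | about 69% | 74% | 75% (n = 54) |
| 20% | 58–61% | 66–67% | 70% (n = 48) |
| 40% | 39–40% | 46–49% | 58% (n = 36) |

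**If treatment also prevents worsening.** Keep q = 40%, but let 75% on placebo and 90% on guselkumab stay at target.

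- Placebo: 0.4 × 0.75 + 0.6 × 0.30 = 48%
- Guselkumab: 0.4 × 0.90 + 0.6 × 0.55 = 69%, so the difference is 21 points
- Simulated power: 64% as planned, 56% restricted, 71% with the added stratum

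Stratifying beat the planned test in every effect scenario run, and type I error stayed at or below 5%. Restricting the denominator helped in some scenarios and hurt in others.

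**The case against.** The best defence is that the SAP describes a status at Week 16 and does not call it improvement. Attainment in all participants is a legitimate endpoint, and it captures prevention of worsening. That stands, and it is why the denominator should not simply be cut down. It does not explain why a known predictor is left out of the test.

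Several stronger readings are tempting, and the documents do not support them:

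- *The components are the SAP's one exception.* They are not. Overall HS-IGA 0 and 0/1 in the same section are also unrestricted.
- *Being at target at baseline guarantees success.* It does not. The participant must be at target at Week 16, and treatment failures and missing values count against.
- *Those at target cannot improve.* This is true only at cut-off 0. Someone at drainage 2 can still fall to 0.
- *The unrestricted test necessarily loses power against a restricted one.* That needs no treatment effect among those at target. The prevention scenario above reverses the order.
- *Large shares are at target.* The documents do not say. HS-IGA is scored at the most severe region at baseline (SAP 5.2.2.4), which limits low scores, and the share must differ between cut-offs and components. The below-3 subgroup refers to the overall score and gives no count.

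It is also fair that the component endpoints are not in the protocol's endpoint list, carry nominal p-values and have no planned power.

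**Conclusion.** The point holds as a modest, low-cost improvement. The comparisons use no baseline information, unlike most of the SAP's other threshold endpoints, so the proportions mix improvement with maintenance and the tests give up some precision. Under the stated assumptions the gain from stratifying is about 5 points of power with 10% at target and roughly 5 to 10 points with 20% to 40%. The sizes are illustrative: the at-target share, the 90% staying rate and the 30% versus 55% rates are all assumptions. A reader might infer that the trial's main efficacy conclusions are at risk. They are not, because HiSCR and the three major secondary endpoints are analysed separately and these tests sit outside the multiplicity procedure.

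**What to change.** In SAP 5.5.6, for each component cut-off and for overall HS-IGA 0 and 0/1:

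1. Keep all participants in the full analysis set and add baseline status on the same score as a CMH stratum, alongside weight and Hurley stage. The split is baseline 0 versus ≥1 for cut-off 0, ≤1 versus ≥2 for 0/1, and ≤2 versus ≥3 for ≤2.
2. Show the Week 16 and over-time proportions by baseline status, so that improvement and maintenance can be read separately.
3. Optionally add a comparison restricted to participants above target, labelled supportive. It should not replace the full comparison, because it discards any effect on worsening and gives each cut-off a different denominator.

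The cost is SAP wording and some extra table rows. No participant is dropped, and no new data are needed, since HS-IGA is scheduled at Week 0 and the form in Protocol Appendix 10 scores each component. Strata become smaller, but the simulated type I error stayed at or below 5%.

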5.5.7. Analysis Related to Patient Reported Outcome

5.5.7.1. DLQI

- The proportions of participants with DLQI score of 0 and 1 at Week 16 for the participants with baseline DLQI score >1 and the proportion of participants with a reduction of 5 or more points in DLQI score for the participants with baseline DLQI score ≥ 5 at Week 16 will be compared between each of the guselkumab groups and the placebo group.
- The change from baseline in DLQI component scores at Week 16 will be compared between each of the guselkumab groups and the placebo group.
- The proportions of participants with DLQI score of 0 and 1 at Week 40 for the participants with baseline DLQI score >1 and the proportion of participants with a reduction of 5 or more points in DLQI score at Week 40 for the participants with baseline DLQI score ≥ 5 will be summarized.

5.5.7.2. Hidradenitis Suppurativa Symptoms Diary (HSSD)

- The change from baseline in each HSSD symptom scale score (7 days recall) and the change from baseline in current pain at Week 16 will be compared between each of the guselkumab groups and the placebo group.
- The change from baseline in HSSD total symptom score at Week 16 will be compared between each of the guselkumab groups and the placebo group.
- Number of participants with a reduction of $\frac{1}{2}$ SD or more from baseline in HSSD total symptom score at week 16 will be compared between each of the guselkumab groups and the placebo group.
- The change from baseline in each HSSD symptom scale score (7 days recall), the change from baseline for the past 24 hours pain and current pain, and the change from baseline in HSSD total symptom score will be summarized over time.

5.5.7.3. Other Patients Reported Outcomes

Hospital Anxiety and Depression

- The change from baseline in Hospital Anxiety and Depression scale (HADs) at Week 16 will be compared between each of the guselkumab groups and the placebo group.
- The change from baseline in Hospital Anxiety and Depression scale will be summarized at Week 16 and Week 40.
- The proportion of participants with hospital anxiety scale <8 and depression scale <8 at Week 16 will be compared between each of the guselkumab groups and placebo groups, among participants with a baseline hospital anxiety scale and depression scale ≥ 8 .
- Hospital anxiety scale and depression scale shift from baseline to Week 16 and Week 40 with respect to the hospital anxiety and depression scale category (<8 , ≥ 8) will be summarized.

Patient's Global Impression of Change (PGIC) of Hidradenitis Suppurativa Severity

- The distribution of the PGIC at Week 16 will be compared between each of the guselkumab groups and the placebo group.

5.5.8. Other

In addition to the above efficacy analyses, the follow efficacy analyses and summaries will be explored by using the observed data without considering treatment failure rules:

- The change from baseline in high-sensitivity-C-reactive protein (hs-CRP) at Week 4, Week 16, and Week 40 will be summarized by treatment groups.
- Hurley stage status shift from baseline to Week 16 and Week 40 will be summarized respectively.

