- The proportion of participants with HS-IGA score of inactive (0) or almost inactive (1) at Week 16 among participants with HS-IGA score of moderate activity (3) or severe activity (4) at baseline.
- The change from baseline in Hospital Anxiety and Depression Scale (HADS) scores at Week 16.
- The change from baseline in high-sensitivity C-reactive protein (hs-CRP) at Week 16.
- The distribution of the Patient Global Impression of Change (PGIC) of HS severity at Week 16.

Refer to Section 8, Study Assessments and Procedures, for evaluations related to endpoints.

HYPOTHESES

The primary hypothesis is that guselkumab treatment is superior to placebo as assessed by the proportion of participants achieving HiSCR at Week 16.

The major secondary hypotheses are that guselkumab treatment is:

- Superior to placebo as assessed by the change from baseline in AN count at Week 16.
- Superior to placebo as assessed by the improvement in patient-reported outcomes (PRO) as measured by:
 - The change from baseline in DLQI score at Week 16.
 - The change from baseline in HS-related pain in the past 24 hours based on HSSD at Week 16.

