Participants who discontinue study intervention due to lack of efficacy or an AE of worsening of HS, or who started a protocol-prohibited medication or therapy during the study that could improve HS are considered treatment failures. The baseline values will be assigned regardless of the observed data for continuous endpoints, zero will be assigned to improvement and percent improvement, and nonresponders status will be assigned to binary response variables. Lesions that received intervention will be counted as present after the visit of intervention. After applying the treatment failure rules, the remaining missing data will be assigned nonresponders status for binary variables. For the longitudinal analyses, missing data handling rules will not be applied.

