9.4.2.3. Other Efficacy Analyses

In addition to the primary and major secondary analyses, the analyses for other efficacy endpoints will be performed and nominal p-values will be provided. The efficacy endpoints (including primary and major secondary endpoints) will also be summarized over time. Additional efficacy analyses may be performed and will be documented in the SAP.

• The proportion of participants achieving at least 50%, 75%, 90%, and 100% reduction in total AN count at Week 16 will be compared between each of the guselkumab groups and the placebo group.

- The proportion of participants achieving an AN count of 1 and 2, respectively at Week 16 will be compared between each of the guselkumab groups and the placebo group.
- The proportion of participants who achieved complete elimination of abscesses at Week 16 will be compared between each of the guselkumab groups and the placebo group.
- The change from baseline in number of abscesses at Week 16 will be compared between each of the guselkumab groups and the placebo group.
- The proportion of participants who achieved complete elimination of draining fistulas at Week 16 will be compared between each of the guselkumab groups and the placebo group among those with draining fistulas at baseline.
- The change from baseline in number of draining fistulas at Week 16 will be compared between each of the guselkumab groups and the placebo group.
- The proportion of participants who achieved complete elimination of inflammatory nodules at Week 16 will be compared between each of the guselkumab groups and the placebo group among those with inflammatory nodules at baseline.
- The change from baseline in number of inflammatory nodules at Week 16 will be compared between each of the guselkumab groups and the placebo group.
- The proportion of participants with HS-IGA score of inactive (0), almost inactive (1), or mild activity (2) and with at least 2-grade improvement relative to baseline at Week 16 will be compared between each of the guselkumab groups and the placebo group.
- The proportion of participants with HS-IGA score of inactive (0), almost inactive (1) at Week 16 among participants with HS-IGA score of moderate activity (3) or severe activity (4) at baseline will be compared between each of the guselkumab groups and the placebo group.

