- The change from baseline in HSSD symptom scale score (other than pain in the past 24 hours) at Week 16 will be compared between each of the guselkumab groups and the placebo group.
- The change from baseline in HSSD total symptom score at Week 16 will be compared between each of the guselkumab groups and the placebo group.
- The change from baseline in HADS at Week 16 will be compared between each of the guselkumab groups and the placebo group.
- The change from baseline in high-sensitivity-C-reactive protein (hs-CRP) at Week 16 will be compared between each of the guselkumab groups and the placebo group.
- The distribution of the PGIC at Week 16 will be compared between each of the guselkumab groups and the placebo group.

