5.2.4.1. Composite Strategy

The Composite Strategy assesses the treatment effects not only based on the variable measurements, but also based on intercurrent event defined in TF criteria. If a participant meets TF criteria, participant will be a non-responder for binary response variables and no improvement will be assigned for continuous variables.

- **Composite Estimand (Continuous)**

Variables: The endpoint is defined as change for baseline score. No improvement (zero change) will be assigned after a subject meets one or more treatment failure criteria.

Intercurrent Events: the intercurrent events are captured through variable definition.

Population level summary: difference in mean changes from baseline between a guselkumab group and placebo group.

- **Composite Estimand (Binary)**

Variables: The endpoint (e.g. HiSCR) is defined as the proportion of participants achieving a response. No responder status will be assigned after a subject meets one or more TF criteria.

Intercurrent Events: the intercurrent events are captured through variable definition.

Population level summary: difference in proportion of responders between a guselkumab group and placebo group.

The composite strategy will be used for analyzing all efficacy endpoints.

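### The protocol promises a Week 16 comparison of hs-CRP with placebo, but the SAP plans only an observed-data summary by group

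*SAP*

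**What the plan says.** **Protocol.** Section 3 lists this among the other secondary endpoints: "The change from baseline in high-sensitivity C-reactive protein (hs-CRP) at Week 16". Section 9.4.2.3 gives the analysis: "The change from baseline in high-sensitivity-C-reactive protein (hs-CRP) at Week 16 will be compared between each of the guselkumab groups and the placebo group". The opening of the same section states the output: "the analyses for other efficacy endpoints will be performed and nominal p-values will be provided". Section 9.4.1 adds that treatment differences come with 95% confidence intervals, and it fixes the handling after treatment failure: "The baseline values will be assigned regardless of the observed data for continuous endpoints".

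**SAP.** Section 5.5.8 is the only place where hs-CRP is analysed as an outcome: "The change from baseline in high-sensitivity-C-reactive protein (hs-CRP) at Week 4, Week 16, and Week 40 will be summarized by treatment groups". The lead-in to that section sets the data handling: "efficacy analyses and summaries will be explored by using the observed data without considering treatment failure rules". The only other use of hs-CRP in the SAP is as a baseline subgroup variable in 2.5. Section 5.2.4.1 closes its account of the estimand with: "The composite strategy will be used for analyzing all efficacy endpoints".

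**The concern.** A contrast that the protocol specifies has become a descriptive table, and the SAP gives no reason. Two things change. First, no model, adjusted difference, confidence interval or nominal p-value is assigned to hs-CRP. Second, values recorded after a participant has met the treatment failure criteria enter as observed, whereas the protocol replaces them with baseline.

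Pharmacodynamics is one of the secondary objectives, and hs-CRP is the only blood marker of inflammation in the endpoint list. The other serum markers go to separate technical reports and may be deferred. If the SAP is followed literally, the study report will not contain the hs-CRP comparison that the protocol says will be made. Anyone who supplies it later will be choosing the model and the failure handling after unblinding.

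**Working it through.** The documents attach no effect size, SD or power to hs-CRP, so there is no figure to reproduce. The check sets the texts side by side.

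| Item | Protocol | SAP |
|---|---|---|
| Status | Other secondary endpoint (1.1, 3) | Absent from the list of other efficacy endpoints in 5.5 |
| Week 16 analysis | Each dose against placebo (9.4.2.3) | Summary by group (5.5.8) |
| Model | MMRM or ANCOVA for continuous endpoints (9.4.1) | 5.5.2.1 assigns MMRM to lesion counts and HSSD, and the 5.4.2.2 approach to DLQI components and HADS; hs-CRP has none |
| Output | Difference, 95% CI, nominal p-value (9.4.1, 9.4.2.3) | Descriptive statistics |
| After treatment failure | Baseline value assigned (9.4.1) | Observed value used (5.5.8), although 5.2.4.1 applies the composite strategy throughout |

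**Is the comparison restored elsewhere in the SAP?** Section 5.1 says that continuous efficacy endpoints are in general compared by MMRM or ANCOVA, and 5.5 promises nominal p-values for other efficacy endpoints. But 5.5 does not list hs-CRP, and the specific text in 5.5.8 speaks of summarising and exploring. Sections 5.5.7.2 and 5.5.7.3 plan explicit comparisons for HSSD, HADS and PGIC, so the SAP says so where it intends one. The general sentences do not clearly bring the comparison back.

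**Is the comparison feasible?** The Schedule of Activities collects hs-CRP at Weeks 0, 4, 16 and 40. There is a post-baseline value before Week 16, which is the condition in SAP 5.2.3.3.2 for using MMRM. Two post-baseline visits through Week 16 give an unstructured covariance matrix with 3 parameters (two variances and one covariance).

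**Does the failure handling bias the summary in a known direction?** For simple means with all values observed, let f be the proportion of an arm in treatment failure, r their mean observed change, and m the mean change in the rest.

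- Observed-data mean change = (1 − f)·m + f·r
- Composite mean change = (1 − f)·m + f·0
- Observed minus composite contrast (guselkumab minus placebo) = f_G·r_G − f_P·r_P

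A negative change is an improvement. If failures are more common on placebo and their hs-CRP falls equally in both arms on prohibited therapy, the term is positive and the apparent drug effect shrinks. If placebo failures stop treatment with rising hs-CRP and guselkumab has few failures, the term is negative and the apparent effect grows. The documents give neither f nor r, so the sign cannot be determined.

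**Does it touch the error rate?** SAP 5.2.1.1 counts 2 comparisons × 4 endpoints = 8 hypotheses. hs-CRP is not among the four endpoints.

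**The case against.** The best defence is that SAP 5.5.8 states its handling openly and that the SAP departs from the failure rules elsewhere too. Section 5.2.3.2.1 exempts the HSSD 7-day pain item, 5.5.2.2 plans observed-data summaries at the Week 16 lock, and 5.5.4 does the same for HiSCR as a sensitivity analysis. A reader might infer from 5.2.4.1 that 5.5.8 uniquely breaks the estimand. The documents do not support that: 5.2.4.1 is a general statement whose exceptions are not cross-referenced, and hs-CRP is one of several. What remains is that for the HiSCR sensitivity analysis the observed-data version sits beside a composite one, while for hs-CRP it stands alone.

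Three other stronger readings also fail.

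- A reader might say that no treatment effect can be obtained. Group means, SDs and group sizes would allow a crude unadjusted difference and interval. What is lost is the adjusted, prespecified contrast.
- A reader might say that the observed-data handling favours guselkumab. The direction is unknown, as shown above.
- A reader might want a log-scale ratio with a stated precision. Neither document plans a log-scale analysis or gives an SD, so any such figure would rest on assumption alone.

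It is also fair to say that replacing a measured laboratory value with baseline is debatable on its merits. That would be a reason to record a departure from protocol 9.4.1, and the SAP records none. The protocol leaves specific details to the SAP, but removing a stated comparison goes beyond supplying detail.

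**Conclusion.** The point holds as a mismatch between the protocol and the SAP. The protocol specifies a Week 16 comparison of hs-CRP for each of the two doses, under the treatment failure rule. The SAP replaces both contrasts with an observed-data summary, assigns no model and gives no reason. The loss is two adjusted differences with their 95% confidence intervals and nominal p-values.

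It is a minor point. hs-CRP is neither a primary nor a major secondary endpoint and would carry nominal p-values only. A reader might infer that the trial's conclusions are at risk, but the alpha allocation, the stated power and the primary and major secondary conclusions are unaffected. The finding rests on the wording of the two documents and needs no numerical assumption.

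**What to change.** - In SAP 5.5, add hs-CRP to the list of other efficacy endpoints.
- In SAP 5.5.2.1, add hs-CRP to the endpoints compared at Week 16: each guselkumab group against placebo, by the MMRM of 5.1 and 5.2.3.3.2 with Weeks 4 and 16, after treatment failure rules, reporting the difference, 95% confidence interval and nominal p-value.
- In SAP 5.5.8, keep the observed-data summary at Weeks 4, 16 and 40 and label it supportive.
- In SAP 5.2.4.1, cross-refer to the analyses that set the failure rules aside.

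A log scale is optional; the documents do not require it, and if it is wanted it should be named before unblinding. If the sponsor instead means to drop the comparison, the SAP should record this as a departure from protocol 9.4.2.3, with the reason, and state the exception in 5.2.4.1.

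The cost is a few lines of SAP text and one table. No new data are needed.
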